APPENDIX 9 NEW YORK HEART ASSOCIATION (NYHA) FUNCTIONAL CLASSIFICATION

Heart failure is usually classified according to the severity of their symptoms. The table below describes the most commonly used classification system, the New York Heart Association (NYHA) Functional Classification. It places patients in one of four categories based on how much they are limited during physical activity.

Class	Patient Symptoms
I	No limitation of physical activity. Ordinary physical activity does not cause undue fatigue, palpitation, dyspnea (shortness of breath).
II	Slight limitation of physical activity. Comfortable at rest. Ordinary physical activity results in fatigue, palpitation, dyspnea (shortness of breath).
III	Marked limitation of physical activity. Comfortable at rest. Less than ordinary activity causes fatigue, palpitation, or dyspnea.
IV	Unable to carry on any physical activity without discomfort. Symptoms of heart failure at rest. If any physical activity is undertaken, discomfort increases.

Class	Objective Assessment
A	No objective evidence of cardiovascular disease. No symptoms and no limitation in ordinary physical activity.
B	Objective evidence of minimal cardiovascular disease. Mild symptoms and slight limitation during ordinary activity. Comfortable at rest.
C	Objective evidence of moderately severe cardiovascular disease. Marked limitation in activity due to symptoms, even during less-than-ordinary activity. Comfortable only at rest.
D	Objective evidence of severe cardiovascular disease. Severe limitations. Experiences symptoms even while at rest.

APPENDIX 10 CONSORT PUBLISHING REQUIREMENTS

The Consolidated Standards of Reporting Trials (CONSORT) encompasses various initiatives developed by the CONSORT Group to alleviate the problems arising from inadequate reporting of randomized controlled trials.

The CONSORT Statement

The main product of CONSORT is the CONSORT Statement, which is an evidence-based, minimum set of recommendations for reporting randomized trials. It offers a standard way for authors to prepare reports of trial findings, facilitating their complete and transparent reporting, and aiding their critical appraisal and interpretation. CONSORT 2010 is the current version of the statement and supersedes the 2001 and 1996 versions.

The CONSORT Statement comprises a 25-item checklist and a flow diagram. The checklist items focus on reporting how the trial was designed, analyzed, and interpreted. The flow diagram displays the progress of all participants through the trial. The checklist and flow diagram are freely available for viewing and downloading at the CONSORT website (<http://www.consort-statement.org/consort-2010>). The CONSORT Statement is endorsed by general medical journals, specialty medical journals, and leading editorial organizations. CONSORT is part of a broader effort, to improve the reporting of different types of health research, and indeed, to improve the quality of research used in decision-making in healthcare.

CONSORT 2010 Guideline

The CONSORT (CONsolidated Standards of Reporting Trials) 2010 guideline is intended to improve the reporting of parallel-group randomized controlled trial (RCT), enabling readers to understand a trial's design, conduct, analysis and interpretation, and to assess the validity of its results. This can only be achieved through complete adherence and transparency by authors. CONSORT 2010 was developed through collaboration and consensus between clinical trial methodologists, guideline developers, knowledge translation specialists, and journal editors (see CONSORT group). CONSORT 2010 is the current version of the guideline and supersedes the 2001 and 1996 versions.

CONSORT “Explanation and Elaboration” Document

The CONSORT “Explanation and Elaboration” document explains and illustrates the principles underlying the CONSORT Statement, and should preferably be used in conjunction with the CONSORT Statement. In addition, extensions of the CONSORT Statement have been developed to give additional guidance for RCTs with specific designs, data and interventions. The CONSORT website (<http://www.consort-statement.org/consort-2010>) contains the current definitive version of the CONSORT 2010 Statement and up-to-date information on extensions.

APPENDIX 11 CHILD-PUGH CLASSIFICATION**Scoring**

The score employs five clinical measures of liver disease. Each measure is scored 1-3, with 3 indicating most severe derangement.

Parameter	Points Assigned		
	1	2	3
Ascites	Absent	Slight	Moderate
Bilirubin (mg/dL)	≤ 2	2 to 3	> 3
Albumin (g/dL)	> 3.5	2.8 to 3.5	< 2.8
Prothrombin Time (seconds over control)	1-3	4 to 6	> 6
INR	< 1.7	1.8 to 2.3	> 2.3
Encephalopathy	None	Grade 1 to 2	Grade 3 to 4

Interpretation

Chronic liver disease is classified into Child-Pugh class A to C, employing the summation of score from above. These scores correlate with one and two year survival:

Points	Class	One year survival	Two year survival
5-6	A (well compensated disease)	100%	65%
7-9	B (significant functional compromise)	80%	60%
10-15	C (decompensated disease)	45%	35%

APPENDIX 12 STATISTICAL METHODOLOGY

DETAILS FOR BAYESIAN LOGISTIC REGRESSION MODEL (BLRM AND BLRM-COPULA), PARTS 1A, 1B, AND BAYESIAN OPTIMAL INTERVAL (BOIN), PART 1C DESIGN

1 BLM MODEL SETUP FOR BMS-986207 MONOTHERAPY

1.1 Monotherapy Methodology Description

An adaptive 2-parameter Bayesian Logistic Regression Model (BLRM) guided by the escalation with overdose control (EWOC) principle^{1,2,3} will be used to guide the dose escalation of BMS-986207 monotherapy in the monotherapy phase, providing dose recommendation during dose escalation.

The BLM will be fitted on the dose-limiting toxicity (DLT) data during the first 4 weeks of treatment accumulated throughout the dose escalation to model the dose-toxicity relationship of BMS-986207 in the monotherapy dose escalation phase.

The dose-toxicity relationships for BMS-986207 monotherapy is assumed to follow a logistic model:

$$\text{logit}(p_i) = \log(a_1) + \beta_1 \log(\frac{d_{1i}}{d_1^*}),$$

where p_i is the probability of toxicity at dose level d_{1i} . Note that the a_1 and β_1 parameters are assumed positive, and d_1^* is the reference dose for BMS-986207 (please refer to the meaning of a_1 and β_1 in Section 1.2.1 for detailed implementation).

1.2 Prior Specification for BMS-986207 Monotherapy

The Bayesian approach requires the specification of prior distributions for model parameters, which include parameters (a_1 , β_1) for BMS-986207. The prior distributions for BMS-986207 single agent activity were derived using a weakly informative prior, as well as discussion with the Bristol-Myers Squibb (BMS) clinical team.

Derivation of prior distribution of these parameters is provided in the following subsections.

1.2.1 Prior Derivation for BMS-986207 Parameters ($\log(a_1)$, $\log(\beta_1)$)

A weakly informative prior will be used for parameters (a_1 , β_1) for BMS-986207 to reflect the potential of the different toxicities of BMS-986207 and allow for considerable prior uncertainty.

Further details are provided below.

Weakly Informative Prior

- The median DLT rate at the reference dose (BMS-986207 at 1600 mg qd) was assumed to be 30%, that is, mean ($\log(a_1)$) = $\text{logit}(0.3) = \log(0.3/(1-0.3)) = -0.847$.
- A doubling in dose was assumed to double the odds of DLT, that is, mean($\log(\beta_1)$) = 0.
- The standard deviation of $\log(a_1)$ was set to 1.53 using the following steps:

- If the toxicity probability range was set to be [1%, 99%], then the toxicity interval would be $\text{logit}(0.99) - \text{logit}(0.01) = 9.19$.
- To cover 99.7% of the variance, the toxicity interval will cover $6 * \text{sd}(\log(a_1))$, which gives us $\text{sd}(\log(a_1)) = 9.19/6 = 1.53$.

Correspondingly, the standard deviation of $\log(\{3_1\})$ was set to 1, which allows for considerably larger prior uncertainty for the dose toxicity.

- 1) The correlation between $\log(a_1)$ and $\log(\{3_1\})$ was set to 0.
- 2) $\log(a_1)$ and $\log(\{3_1\})$ follow a bivariate normal distribution.

Table 1: Prior Distribution for Model Parameters for BMS-986207

Parameter	Means	Standard Deviations	Correlation
$\log(a_1)$, $\log(\beta_1)$	(-0.847, 0)	(1.53, 1)	0

2 BLRM MODEL SETUP FOR BMS-986207 AND NIVOLUMAB COMBINATION

2.1 Methodology Description for Combination Therapy

Toxicity profiles of both BMS-986207 monotherapy and nivolumab monotherapy will be incorporated to develop the combination model framework. A copula-type model will be used to cover all general combination cases, including additive and synergistic effects. The combination of the 2 treatments will be explored using a Bayesian hierarchical model by utilizing the toxicity profiles of the single agents as prior marginal profiles for the combination. The following copula-type model⁴ will be used to describe the probability p_{ij} of toxicity when dose level i of agent A and dose level j of agent B are administered in combination:

$$p_{ij} = 1 - \exp(-[\{-\log(1 - p_i)\}^{1/m} y_1 + \{-\log(1 - q_j)\}^{1/n} y_1]),$$

where p_i is the prespecified best guess toxicity probability for agent A, q_j is the prespecified best guess toxicity probability for agent B, m and n characterize the individual drug effect, and y_1 characterizes the drug-drug interactive effect.

The joint toxicity framework models the toxicity rates of both agents as well as their interaction effects in a 7-parameter hierarchical model, where each monotherapy dose-toxicity relationship will be characterized by a 2-parameter BLRM model (see [Section 1.1](#)). There are 3 additional parameters for the copula-type model, 1 for each agent (m and n) as well as 1 for the interaction term (y_1). A dose-toxicity surface will be characterized for different dose combinations of these 2 agents.

As there are currently no historical data or prior knowledge to indicate how much information is to be borrowed for each of the single agents, parameters m and n are both set to be 1, meaning

borrowing 100% of the information from the 2 agents. The above formula is then simplified into a 5-parameter model as follows:

$$p_{ij} = 1 - \exp(-[\{-\log(1 - p_i)\}^{1/y_1} + \{-\log(1 - q_j)\}^{1/y_1}]^{1/y_1}).$$

Since only a fixed nivolumab dose (240 mg) will be used in the BMS-986207 and nivolumab combination, this surface will be simplified into a 2-dimensional dose-toxicity curve. Posteriors for the corresponding 5 parameters (2 logistic regression parameters [a_1 , $\{3_1\}$ for BMS-986207 and 2 logistic regression parameters [a_2 , $\{3_2\}$ for nivolumab, as well as 1 interaction parameter for the copula-type model [y_1 , which will be discussed in detail in the following section]) will be fitted into the in-house developed model. It implements the above-described theoretical setup.

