5.1.2.3 Preliminary Safety Cohort & Dose Escalation (Part 1A and 1B)

Approximately 35 participants are expected to be treated during each dose escalation part of the study guided by Bayesian Logistic Regression Model (BLRM). Each participant will be administered IV doses of BMS-986207 per the cohort assignment as follows:

- The Preliminary Safety Cohort precedes participant enrollment in Monotherapy - Dose Escalation (Part 1A) of the study. The first participant enrolled into monotherapy escalation will receive BMS-986207 starting at the 2 mg dose level, followed 2 weeks later with intra-participant dose escalation to the 6 mg dose level, followed 2 weeks after that with intra-participant dose escalation to the 20 mg dose level. This first participant will be subject to a 5-day safety observation period after receiving the first 20 mg dose. No other intra-participant dose escalation is planned for this study. If there are no DLTs or other safety concerns observed, an additional 2 participants will be enrolled in the 20 mg dose cohort. Please refer to [Appendix 13](#) for complete details of the Preliminary Safety Cohort
- In Part 1A (monotherapy dose escalation), the planned flat dose levels for BMS-986207 are 20, 80, 240, 800 and 1600 mg (assuming an 80kg participant) q2w, in 8-week cycles, for up to 3 cycles of study therapy (24 weeks). In addition, a q4w schedule of BMS-986207 will be evaluated at flat doses of 480 mg and 1600 mg (assuming an 80kg participant). Enrollment of the first q4w cohort will be guided by the safety, PK, [REDACTED] analysis from the q2w cohorts. Following each treatment cycle, the decision to treat a participant with additional cycles of study therapy (up to a maximum of 6 cycles), will be based on tumor assessment at the end of each cycle.
- In Part 1B, (combination therapy dose escalation), BMS-986207 and nivolumab will be administered at flat doses of 80 and 240 mg BMS-986207 q2w with 240 mg nivolumab q2w. In addition, BMS-986207 will be administered at flat doses of 480 and 1600 mg q4w in combination with nivolumab administered at 480 mg q4w. Study drugs will be administered in 8-week cycles, for up to 3 cycles of study therapy (24 weeks). Following each treatment cycle, the decision to treat a participant with additional cycles of study therapy (up to a maximum of 6 cycles), will be based on tumor assessment at the end of each cycle.

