5.1.2.4 Dose Escalation Decisions for Monotherapy and Combination (Parts 1A and 1B)

The dose escalation phase of the study will evaluate the safety and tolerability of BMS-986207, given alone or in combination with nivolumab, based on DLTs, using a BLRM model (for BMS-986207 as monotherapy) and a BLRM-copula model (for BMS-986207 in combination with nivolumab).

Combination dose escalation (Part 1B) will not begin until 3 dose cohorts (i.e., 20 mg, 80 mg and 240 mg) have been determined to be safe in monotherapy dose escalation (Part 1A). During the dose escalation phase, a set of approximately 3 participants will be treated at each specified dose level. Cohort tolerability assessment and subsequent dose recommendation will occur when at least 2 evaluable participants within a cohort have completed a 4-week DLT period. Any toxicities that occur beyond the 4-week DLT period will be accounted for in making dose level decisions and/or dose level modifications.

If the potential DLT occurring in the third evaluable participant regarding the specific dose level does not influence the dose recommendation by BLRM or the BLRM-Copula model, the next dose level may proceed without waiting for the third participant to complete the corresponding DLT observation period, after discussion and agreement between the Sponsor and Investigators. Continuous re-assessment of dose recommendation, by BLRM in the escalation phase and BLRM-Copula in the combination phase, will be carried out for each dose level. Planned dose levels for dose escalation are provided in [Table 5.1.2.4-1](#). Planned dose levels may be modified, or intermediate dose levels added, based upon the BLRM analysis.

Table 5.1.2.4-1: Planned Doses During Part 1B (Combination Dose Escalation)

Dose Level/Cohort	BMS-986207	Nivolumab	Dose Schedule
1	80 mg	240 mg	q2w
2	240 mg	240 mg	q2w
3	480 mg	480 mg	q4w
4	1600 mg	480 mg	q4w

The RP2D dose of BMS-986207, alone and in combination with nivolumab, selected for cohort expansion will be based on evaluating the recommendation from BLRM and an overall assessment of all available safety, PK/█ and efficacy data.

Once the safety (during DLT evaluation) of a dose level has been established (Part 1A and/or Part 1B), additional participants (up to a total of 15) may be added to that dose level, to better characterize the PK, safety █ profiles █ assessments.

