3.2 Simulation Parameters

One thousand trial simulations were used for each scenario. All simulations were run using EAST 6.3.1® software for BLRM model for BMS-986207 monotherapy and in-house developed code via R and Openbugs for BLRM-copula method for BMS-986207 in combination with nivolumab. The number of subjects to be treated in each cohort in a specific dose level and the stopping rules used to declare MTD are defined as:

- Fixed cohort size: 3
- Probability of overdosing: < 30%
- Probability of achieving the target toxicity: > 50%
- Maximum number of participants treated: 30
- Minimum number of participants treated at a given dose level in order to declare MTD: 6
- Maximum number of participants at a dose: 12

The provisional dose levels for BMS-986207 monotherapy are 80-1600 mg. For the combination therapy, nivolumab is fixed at 240 mg flat dose for q2w.

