Table 5: **Simulation Results of BLRM-copula for Various Doses of BMS-986207 in Combination with Nivolumab 240 mg q2w**

Scenario	BMS-986207 Dose	80	240	800	1600	MTD not selected (%)	Fitted MTD	Toxicity Observed (%)	Avg # Pts
Additive	% DLT	10	14	25 ^a	40				
	% MTD	3.9	30.3	51.4	11.2	3.2	1335	20.0	19.9
	# Pts	4.3	5.0	8.4	2.2				
25% higher	#DLT	0.4	0.7	2.0	0.9				
	% DLT	13	18 ^a	32 ^a	50				
	% MTD	8.0	39.8	43.4	2.6	6.2	1019	30.0	18.4
50% higher	# Pts	4.8	5.8	6.7	1.1				
	#DLT	0.6	1.0	2.0	0.6				
	% DLT	15	21 ^a	38	60				
	% MTD	10.8	49.8	27.5	0.5	11.4	788	30.0	17.2
	# Pts	5.1	6.2	5.3	0.6				
	#DLT	0.8	1.3	2.0	0.3				

% DLT, true DLT rate; % MTD, proportion of the dose selected as the MTD; #DLT, average number of DLTs; MTD not selected: dose was below lowest dose or above highest dose; Fitted MTD: fitted MTD at 30% as the target toxicity rate and the dose range falls into the target toxicity range of [16%, 33%]; Toxicity observed: Average proportion of DLTs out of all simulated trials; # Pts, average number of participants

^a Doses with true target toxicity within the target toxicity interval [16%, 33]

The average sample size was no more than 20 participants. The results show how the EWOC principle limits the risk of exposing participants from unacceptable toxic dose levels, eg, 50% or above. Overall, the scenarios illustrated above demonstrate that the model performs well by correctly identifying the MTD ranging from 50% to 83% in the hypothetical scenarios investigated while limiting participants from receiving unacceptable toxic dose levels

4 BLRM INTERIM MONITORING CASE STUDY TO ILLUSTRATE PROVISION OF DOSE RECOMMENDATIONS DURING DOSE-ESCALATION

[figure not shown]
In order to provide a comprehensive view of the dynamics of the models, different hypothetical scenarios exploring all possibilities are examined. For the simplicity of illustration purposes, a static cohort size of 3 subjects is applied for dose levels 80 mg, 240 mg, 800 mg and 1600 mg in the BMS-986207 monotherapy and for the dose level 80 mg in the combination setting. This cohort size could vary during the actual clinical trial, and the BLRM (-Copula) models are designed to fit various different cohort sizes, adaptively. In general, there are 4 possible scenarios for a specific dose level, which are 0 DLT observed in 3 total subjects in that cohort (denoted as 0/3), 1 DLT

observed in 3 subjects (1/3), 2 DLTs observed in 3 subjects (2/3), and 3 DLTs observed in 3 subjects (3/3).

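### The combination-model operating characteristics in Appendix 12 were computed for a q2w-only ladder with nivolumab fixed at 240 mg, not for the Part 1B ladder the protocol plans

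*Combined protocol and SAP*

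**What the plan says.** Appendix 12, Section 2.1 collapses the two-drug toxicity surface to one curve with this premise: "Since only a fixed nivolumab dose (240 mg) will be used in the BMS-986207 and nivolumab combination". Section 3.2 of that appendix repeats it for the simulations ("For the combination therapy, nivolumab is fixed at 240 mg flat dose for q2w"). Table 5 is titled "Simulation Results of BLRM-copula for Various Doses of BMS-986207 in Combination with Nivolumab 240 mg q2w" and uses 80, 240, 800 and 1600 mg. The explanation of Figure 1 also describes a slice with nivolumab held at 240 mg.

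The design sections say otherwise. Section 5.1.2.3 states that "BMS-986207 will be administered at flat doses of 480 and 1600 mg q4w in combination with nivolumab administered at 480 mg q4w". Table 5.1.2.4-1 lists four Part 1B levels: 80 mg q2w, 240 mg q2w, 480 mg q4w and 1600 mg q4w, with nivolumab 240, 240, 480 and 480 mg. Section 5.1.2.4 puts this ladder under the BLRM-copula and adds: "The RP2D dose of BMS-986207, alone and in combination with nivolumab, selected for cohort expansion will be based on evaluating the recommendation from BLRM", together with the other safety, PK and efficacy data.

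Appendix 12, Section 3.3.2 concludes from Table 5 that the model identifies the MTD correctly in 50% to 83% of trials with an average of no more than 20 participants. Section 10.1.1 cites the appendix for that expected size.

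**The concern.** The premise used to simplify the model is false for two of the four planned levels, and the simulated grid is not the planned grid. Section 3.2.1.4 reports 30 combination participants as of 21-Jan-2021, of whom 18 + 4 = 22 received the q4w regimens. Most of the Part 1B experience therefore lies outside the setting that was simulated.

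The model in Appendix 12, Section 1.1 takes dose in mg relative to a 1600 mg reference and carries no schedule term, and the reference is labelled with a daily schedule used nowhere in the study. The DLT window is 28 days, which holds two q2w doses or one q4w dose. A reader cannot tell what dose value a q4w cohort contributes. MTD/RP2D is a primary objective for these parts and the model recommendation feeds it, so the performance claimed for the model should belong to the design in use.

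**Working it through.** **1. The plan's own figures.** From Table 5, selection of in-target levels is 51.4% (additive), 39.8 + 43.4 = 83.2% (25% higher) and 49.8% (50% higher). Average N is 19.9, 18.4 and 17.2. These match the stated range.

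The copula model was re-simulated from the published settings: cohorts of 3; P(DLT rate ≥ 33%) below 30%; stop at 6 or more participants with P(target) above 50%; at most 12 per dose and 30 in all; 2,000 trials per scenario. The gamma shape of the interaction prior (about 13.5) was solved from its stated mean of 1.1 and 40% probability below 1.

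- Dose skipping allowed: 50.2%, 82.4% and 53.2% correct; N = 18.1, 17.3 and 16.5.
- No skipping: 47.6%, 80.9% and 50.3% correct; N = 18.5, 17.1 and 15.8.

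The range reproduces. The largest gap is 3.8 points in selection and about 2 participants in N. The sponsor's code is in-house, so exact agreement is not expected.

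**2. The two ladders.**

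| | Level 1 | Level 2 | Level 3 | Level 4 |
|---|---|---|---|---|
| Simulated (Table 5) | 80 q2w | 240 q2w | 800 q2w | 1600 q2w |
| Planned (Table 5.1.2.4-1) | 80 q2w | 240 q2w | 480 q4w | 1600 q4w |
| Planned, mg in 28 days | 160 | 480 | 480 | 1600 |
| Nivolumab planned, mg in 28 days | 480 | 480 | 480 | 480 |

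By 28-day total, planned levels 2 and 3 coincide, and level 4 equals 800 mg q2w (2 × 800 = 1600).

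**3. Planned ladder, additive scenario.** q4w doses are entered as nominal mg, the direct reading of the written model, with nivolumab constant. True rates are assumed from Table 5 in two ways.

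- *Risk follows 28-day dose:* true rates 10/14/14/25%. Selection is 2.7/8.6/73.1/12.1%. The only level within 16% to 33% is chosen about 12% of the time (about 8% if nivolumab is also entered as nominal mg). Entering the 28-day equivalents 80/240/800 instead gives 59%.
- *Risk follows nominal mg:* the rate at 480 mg is interpolated on the logit scale in log dose. The fraction is log(480/240)/log(800/240) = 0.576, so logit = −1.815 + 0.576 × 0.717 = −1.403, or 19.7%. True rates are 10/14/19.7/40%, and the in-target level (480 mg) is chosen 76.5% of the time.

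**4. Planned ladder, 50% higher scenario.** With 28-day truth (15/21/21/38%), correct selection is 17.7 + 58.3 = 76.0%. With nominal truth (15/21/30.1/60%), it is 24.8 + 51.3 = 76.1%. Table 5 states 49.8%. Average N is 16.1 and 15.4, against 17.2 stated.

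**5. Effect of coding on one decision.** With the illustrative priors of Appendix 12 and 0/3 DLTs at both 80 and 240 mg, P(DLT rate ≥ 33%) for 1600 mg q4w is 0.385 entered as 1600 mg and 0.123 entered as its 800 mg q2w equivalent. The cap of 0.30 lies between them.

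**The case against.** **Total 28-day mg is not clearly the better scale.** Amendment 04's rationale table gives a 14-day half-life. Under one-compartment elimination, exposure over days 0 to 28 is proportional to 480 × 0.75 = 360 for a single 480 mg dose, and to 240 × 0.75 + 240 × 0.50 = 300 for 240 mg on days 1 and 15. That is 20% more for the single dose, with twice the initial peak. Ranking 480 mg q4w above 240 mg q2w is therefore defensible. This stands, and it rules out mandating one metric.

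**A constant nivolumab term can be defended.** Section 5.5.2.2 expects 240 mg q2w and 480 mg q4w to give similar exposure, and the note to Appendix 12, Table 3 says the nivolumab prior will be revisited if PK departs from the mg/kg assumption. This stands too, but Appendix 12 justifies the constant by a single dose, not by exposure.

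**The scope is partly disclosed.** Table 5's title names nivolumab 240 mg q2w, and the conclusion is limited to hypothetical scenarios. However, nothing warns that the planned ladder differs, and Section 10.1.1 relies on the results.

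**Stronger readings that the documents do not support.**

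- A reader might infer that the model treats equal 28-day doses as different. Nominal mg is the natural reading, but the q4w coding is never stated, and Section 5.5.2.1 shows awareness of the schedule relation by deriving q4w doses linearly from q2w.
- A reader might put the prior DLT rate at 6.0% for 240 mg and 11.4% for 480 mg. Those values come from inserting the parameter means. Under Table 1 of Appendix 12 the medians are about 4.3% and 8.4%, with 95% intervals of roughly 0 to 69% and 0 to 76%. Section 2.2.1 also replaces this prior with the monotherapy posterior.
- In the written model, 1600 mg q2w and 1600 mg q4w share one dose value in Part 1A. But Section 3.2.1.4 lists only q2w monotherapy (3 + 3 + 4 + 28 + 4 = 42), so no such pooling is on record.

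**Conclusion.** The point holds as a mismatch between Appendix 12 and Section 5. The single-dose premise is contradicted by current text, and the 50% to 83% figure was not evaluated for the planned ladder. In the additive scenario, correct selection there could be anywhere from about 12% to about 77%, against 51.4% stated. Those values rest on the assumed true rates, nominal-mg coding, the solved gamma shape and a re-simulation accurate to a few points.

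The direction is not fixed: in the 50% higher scenario the planned ladder does better than stated (about 76% against 49.8%). The 12% result also reflects selection of 480 mg q4w, whose assumed rate of 14% lies just under the 16% floor, so it is not a finding of overdosing. The sample-size statement is less exposed, since average N moves little where checked.

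It would be wrong to infer that the MTD/RP2D itself is in error. No recommendation is shown to have changed, the final choice uses all safety, PK and efficacy data, all four Part 1B levels had been dosed by January 2021, and Part 1C uses a different design. The importance is low and the correction cheap.

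**What to change.** - Reconcile Appendix 12 (Sections 2.1 and 3.2, Table 5 and the Figure 1 explanation) with Section 5.1.2.3 and Table 5.1.2.4-1.
- Re-run the BLRM-copula operating characteristics on the planned ladder (80 and 240 mg q2w, 480 and 1600 mg q4w). Otherwise state that Table 5, the 50% to 83% figure and the expected size cited in Section 10.1.1 apply only to the q2w set.
- State how a q4w dose enters the model, and justify the constant nivolumab term from the exposure argument in Section 5.5.2.2.
- Report the final model-based MTD under both nominal-mg and 28-day-mg coding as a sensitivity analysis, without imposing either.

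The cost is an appendix edit, one simulation run and two fits to existing data. No new data are needed.
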